6.5 Appendix 5: Methods to Manage Missing Data

Observed data is used for analysis, unless handling of missing data is described otherwise within the analysis description or in the sections below.

6.5.1 Missing Date Information for Adverse Events

If the AE start date is missing, and the AE stop date is on or after the first dose of study medication, then the AE start date will be imputed as the date of the first dose of study medication.

If the AE start date is missing, and the AE stop date is not missing and before the first dose of study medication, then the AE start date will be imputed as the stop date.

Partial AE Start Date

Missing day and month

- If the year is the same as the year of the date of the first dose of study medication, then the day and month of the date of the first dose of study medication will be assigned to the missing fields.
- If the year is before the year of the date of the first dose of study medication, then December 31 will be assigned to the missing fields.
- If the year is after the year of the date of the first dose of study medication, then January 1 will be assigned to the missing fields.

Missing month only

- The day will be treated as missing and both month and day will be replaced according to the above procedure.

Missing day only

- If the month and year are the same as the month and year of the date of the first dose of study medication, then the day of the first dose of study medication will be assigned to the missing day.
 - If either the year is before the year of the date of the first dose of study medication or if both years are the same but the month is before the month of the date of the first
-

dose of study medication, then the last day of the month will be assigned to the missing day.

- If either the year is after the year of the date of the first dose of study medication or if both years are the same but the month is after the month of the date of the first dose of study medication, then the first day of the month will be assigned to the missing day.

If the imputed AE start date is after the AE stop date, then the imputed AE start date will be set to the AE stop date.

6.5.2 Missing Date Information for Concomitant Medications

If the medication start date is missing, and the medication stop date is on or after the first dose of study medication, then the medication start date will be imputed as the date of the first dose of study medication.

If the medication start date is missing, and the medication stop date is not missing and before the first dose of study medication, then the medication start date will be imputed as the medication stop date.

Partial Medication Start Date

Missing day and month

- If the year of the incomplete start date is the same as the year of the date of the first dose of study medication, then the day and month of the date of the first dose of study medication will be assigned to the missing fields.
- If the year of the incomplete start date is before the year of the date of the first dose of study medication, then December 31 will be assigned to the missing fields.
- If the year of the incomplete start date is after the year of the date of the first dose of study medication, then January 1 will be assigned to the missing fields.

Missing month only

- The day will be treated as missing and both month and day will be replaced according to the above procedure.

Missing day only

- If the month and year of the incomplete start date are the same as the month and year of the date of the first dose of study medication, then the day of the first dose of study medication will be assigned to the missing day.
 - If either the year is before the year of the date of the first dose of study medication or if both years are the same but the month is before the month of the date of the first dose of study medication, then the last day of the month will be assigned to the missing day.
-

- If either the year is after the year of the date of the first dose of study medication or if both years are the same but the month is after the month of the date of the first dose of study medication, then the first day of the month will be assigned to the missing day.

Partial Medication Stop Date

If a medication stop date is missing and the ongoing status is also missing, then the medication is assumed to be ongoing.

If the imputed medication stop date is before the medication start date (whether imputed or non-imputed), then the imputed medication stop date will be equal to the medication start date.

Missing day and month

- If the year of the incomplete stop date is the same as the year of the date of the last dose of study medication, then the day and month of the date of the last dose of study medication will be assigned to the missing fields.
- If the year of the incomplete stop date is before the year of the date of the last dose of study medication, then December 31 will be assigned to the missing fields.
- If the year of the incomplete stop date is after the year of the date of the last dose of study medication, then January 1 will be assigned to the missing fields.

Missing month only

- The day will be treated as missing and both month and day will be replaced according to the above procedure.

Missing day only

- If the month and year of the incomplete medication stop date are the same as the month and year of the date of the last dose of study medication, then the day of the last dose of study medication will be assigned to the missing day.
- If either the year is before the year of the date of the last dose of study medication or if both years are the same but the month is before the month of the date of the last dose of study medication, then the last day of the month will be assigned to the missing day.
- If either the year is after the year of the date of the last dose of study medication or if both years are the same but the month is after the month of the date of the last dose of study medication, then the first day of the month will be assigned to the missing day.

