9.10 Compliance

All study drugs will be administered in the clinic and documented in the source and recorded in the eCRF.

SUBLOCADE compliance will be assessed by inspecting the injection site for evidence of attempted removal of the depot by the subject, documented in the source and recorded in the eCRF. Likewise, surgical removal by a physician will be documented in the source and recorded in the eCRF. See Section [10.7](#) for details on reporting depot removal.

Use of prohibited concomitant medications will be evaluated per the Concomitant Medication assessment outlined in the [Table 1](#) and [Table 2](#), documented in the source and recorded in the eCRF.

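### SAP 6.5.2 can impute a medication start date later than a stop date known to precede dosing, so Table 12 may mislabel medicines that had already ended (minor)

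*SAP*

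**What the plan says.** SAP Section 6.5.2 treats wholly missing and partial medication start dates separately.

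- **Wholly missing start, stop before the first dose:** "then the medication start date will be imputed as the medication stop date". The result agrees with the stop date.
- **Year-only start in the dosing year:** the condition reads "If the year of the incomplete start date is the same as the year of the date of the first dose of study medication". When it is met, the gaps are filled so that the start falls on the dosing day.
- **Month and year known, same month as dosing:** "then the day of the first dose of study medication will be assigned to the missing day".

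Neither partial-start rule refers to the stop date. The only ordering rule in 6.5.2 concerns the stop: when an imputed stop falls before the start, "then the imputed medication stop date will be equal to the medication start date". It applies even if that start was itself imputed.

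Section 6.5.1 has nearly the same start-date rules for adverse events, but closes with a check in the other direction: when the imputed start is later than the stop, "then the imputed AE start date will be set to the AE stop date".

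Table 12 (SAP Section 6.8) classifies each medicine against the first TM BUP induction dose. An end before that dose with a start on or after it is *Data Error*. An end and a start both on or after it is *Concomitant* only. Where a time is missing, dates alone are compared.

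**The concern.** The partial-start rules choose the latest date that keeps the medicine from starting after dosing. That is harmless when the medicine was still being taken at dosing. When the record itself shows that it ended earlier, the rule produces a start after the stop. Section 6.5.1 anticipates this for adverse events; 6.5.2 does not. Where the stop is also partial, the ordering rule lets a guessed start override a reported stop month.

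Such records can be expected. The schedule of assessments collects medicines taken within 30 days before consent (Protocol Table 1, note 7), and screening runs from Day -30 to Day -1. Concomitant medication is a stated safety endpoint (Protocol Section 3.3), and SAP Section 5.5.8.4 summarises it by number and percentage of subjects. At stake is whether a medicine finished before dosing is tabulated as prior use, as use on study drug, or as an error.

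**Working it through.** The plan gives no figure on this point. The check applies the 6.5.2 rules and Table 12, as written, to imputed dates.

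**Inputs.** The rules above, plus one assumption: first and last study dose both on 15 October 2019. The date is illustrative, but SAP Section 5.6 places re-training on 08Oct2019, so it is realistic. A partial stop in a month before the last dose becomes the last day of that month.

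**Worked records**

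| Reported start | Reported stop | Imputed start | Stop used | Table 12, as written | With start capped at stop |
|---|---|---|---|---|---|
| 2019 | 20 Sep 2019 | 15 Oct 2019 | 20 Sep 2019 | *Data Error* | *Prior* |
| Oct 2019 | 10 Oct 2019 | 15 Oct 2019 | 10 Oct 2019 | *Data Error* | *Prior* |
| 2019 | Sep 2019 | 15 Oct 2019 | 30 Sep, then moved to 15 Oct 2019 | *Concomitant* | *Prior* |
| 2018 | 20 Sep 2019 | 31 Dec 2018 | 20 Sep 2019 | *Prior* | *Prior* |
| 2018 | 10 Jun 2018 | 31 Dec 2018 | 10 Jun 2018 | *Prior* (dates out of order) | *Prior* |
| 2019 | 20 Oct 2019 | 15 Oct 2019 | 20 Oct 2019 | *Concomitant* | *Concomitant* |

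The first three rows are wrong as written. The next two show that a partial start in an earlier year does not change the label. The last shows that the cap leaves a medicine continuing past dosing alone.

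**Which date patterns trigger it.** Take every pair of true dates with start in 2019, start on or before stop, and stop in the 60 days before dosing. There are 287 days from 1 January to 14 October. The first 228 start days each allow 60 stop days and the last 59 allow 59 down to 1, so the number of pairs is 228 × 60 + (59 × 60)/2 = 13,680 + 1,770 = 15,450.

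- Year-only start, complete stop: 15,450 of 15,450 are *Data Error*.
- Year-only start, stop known only to a month before October: drop the 14 October stop days, which account for 274 + 275 + … + 287 = 3,927 pairs. That leaves 15,450 − 3,927 = 11,523, all *Concomitant*.
- Month-and-year start, complete stop: wrong only when the medicine started and stopped within 1 to 14 October, which is 14 × 15/2 = 105 pairs, or 105/15,450 = 0.7%. All are *Data Error*; the rest are *Prior*.
- Month-and-year start, stop known only to a month before October: all 11,523 are *Prior*.

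With the start capped at the stop, every record in the grid is *Prior*.

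**Size in the tables.** Rows count subjects, so one wrong label changes a row by at most one subject: 1/15 = 6.7 percentage points with 15 injected subjects.

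**The case against.** The strongest objection is that the SAP never says Table 12 uses imputed dates. The table has its own row and column for missing dates, and Sections 5.5.8.4 and 6.8 expect some medicines to be both prior and concomitant because dates are missing. That suggests a table written for reported dates. This stands as an ambiguity but does not remove the problem. A partial date is not a missing one and must be resolved before it can be compared with the dose, and SAP Sections 5.5 and 5.5.8 refer to Section 6.5 for that. Nor is it safe to read the wholly-missing rule as covering partial dates: these have their own sub-heading, and 6.5.1 needed its cap despite having the same wholly-missing rule.

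Several stronger inferences are tempting but not supported:

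- **Such records drop out of both tables.** The SAP does not say what happens to a record labelled *Data Error*. Protocol Section 13.2 provides for checks and site queries, and SAP Section 5.5.8.4 lists the medications.
- **Judgement of prohibited-medication use is distorted.** Protocol Section 9.10 says "Use of prohibited concomitant medications will be evaluated per the Concomitant Medication assessment", with documentation in source and eCRF. It does not rely on imputed dates or Table 12 labels.
- **The error rate is 100%.** That figure only restates the rule for records chosen to trigger it.
- **Every wrong label costs 6.7 points.** It costs nothing if the subject already counts in that row through another record.
- **A wholly missing start with a stop on or after dosing is a further error.** Section 6.5.2 would make it *Concomitant* only, and Table 12's missing column would make it both. This is the same ambiguity about which dates the table uses.
- **Moving the stop to the start is always wrong.** With first and last dose on 20 October 2019, a start of November 2019 and a stop of 2019 impute to 1 November and 20 October. Moving the stop to 1 November is right; an unrestricted cap would move the start to October, against the reported month.

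**Conclusion.** The gap is real and minor. For two partial-start patterns, 6.5.2 can place a medicine's start after a stop known to precede dosing. If Table 12 is then applied to the imputed dates, the label is *Data Error* with a complete stop, or *Concomitant* with a year-only start and a stop in an earlier month; *Prior* is correct in both. The conclusion rests on that use of imputed dates, which the SAP implies but does not state. It does not depend on the illustrative dosing date, only on the partial start sharing the year, or the month and year, of the first dose.

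The number of affected records cannot be estimated, because neither document gives the frequency of partial dates. Only the descriptive prior and concomitant medication tables are touched, in a study without hypothesis tests (SAP Section 2). The COWS, OC-VAS, NMP and adverse-event analyses are unaffected.

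**What to change.** Add to SAP Section 6.5.2, ahead of the stop-date ordering rule:

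*If the stop date as reported (complete, or partial with a known month or year before that of the first dose) precedes the first dose of study medication, and the imputed start date is after the reported or imputed stop date, set the start date to the stop date, provided this does not contradict the reported parts of the start date.*

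Keep the present stop-date rule for all other cases. The limited cap gives *Prior* for the three wrong records above and for the whole grid, since every stop there is known to precede dosing and the moved start keeps its reported year or month. It does not act on the November 2019 example, where the stop is not known to precede dosing.

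Also state whether Table 12 uses reported or imputed dates, so that a wholly missing start is handled the same way in 6.5.2 and in the table.

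Cost: a few sentences in the SAP and one programming change. No new data are needed.

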6.6 Appendix 6: Methods to Manage Character Values of Clinical Laboratory Tests

If the reported value of a clinical laboratory parameter cannot be used in a statistical summary table due, for example, to the fact that a character string is reported for a parameter of the numerical type, a derived value will be assigned and used in the statistical analyses. The reported value will be presented in data listings.

The reported and derived values will be assigned prior to DBL and will be noted in the ADaM Reviewer’s Guide.

6.7 Appendix 7: Demographic and Baseline Characteristics

Demographic and disease characteristics at screening (age, sex, race, ethnicity, weight, height, BMI, tobacco use, caffeine use and drugs of abuse, baseline disease history (i.e., Screening visit UDS, COWS and OC-VAS)) will be summarised for the subjects who did not enroll, the Enrolled Population, the FAS and the safety analysis set using descriptive statistics.

6.8 Appendix 8: Prior and Concomitant Medications

The definitions for prior and concomitant medications are found in Table 12. The assignments will be made relative to the date/time of first TM BUP dose in the induction phase.

Note that a given medication may be considered both prior and concomitant depending on missing start and end dates/times, under these definitions. Therefore, the prior/concomitant medication categories are not mutually exclusive.

Table 12 Definitions of Prior and Concomitant Medications

End Date/Time of Non-Study Medication	Start Date/Time of Non-Study Medication		
	Missing ¹	< Start date/time of Study Medication ²	≥ Start date/time of Study Medication ²
Missing (includes flagged as ‘Ongoing’) ¹	Prior Concomitant	Prior Concomitant	Concomitant
< Start date/time of Study Medication ²	Prior	Prior	Data Error
≥ Start date/time of Study Medication ²	Prior Concomitant	Prior Concomitant	Concomitant

¹ If the time is missing, then only the date will be used.

²Date/time of first TM BUP dose in the induction phase.

